## **Outcome Measures and Analysis:**

AUTO Study Protocol: Version Date: 12/22/21 PI: [name], MPH COMIRB No: 19-0059 Key measures in this trial (Table 3, additional details below) are tied directly to our theoretical framework (Figure 1) and assess DDA effects (Aim 1) and potentially differential subgroup effects (Aim 2).

Immediate outcomes: Our primary outcome will be the DDA's effect on decision quality, a fundamental element of the Ottawa Decision Support Framework as a precursor to behavior change (Figure 1). A high quality decision is defined as an informed patient making a decision consistent with their values.

-Decision Conflict: The Decisional Conflict Scale (DCS) measures internal conflict or ambivalence about the decision, with higher internal conflict (or ambivalence) indicating the decision is less in-line with personal values. The DCS is closely linked to overall decision quality and is a recommended primary outcome measure. The DCS estimates decisional conflict through personal perceptions of issues such as uncertainty in choosing options, modifiable factors contributing to uncertainty, and effective decision-making (e.g., expressing satisfaction with the choice). The DCS is a 16-item scale (with Likert scale response options) that has high reliability and test-retest correlation (Cronbach's alpha coefficients > 0.78). In prior work, the DCS has been shown to discriminate between known groups who make or delay decisions (effect size 0.4-0.8), with lower scores indicating low decision conflict (and greater likelihood of implementing a decision). Scores <25 (out of 100 total) are associated with implementing decisions.

-Values Concordance: We will use the "Values Clarity" subscale of the DCS to examine specifically how much participants feel their decisions are in line with their values. Three DCS items are summed and multiplied by 8.33; scores range from 0 (extremely clear) to 100 (extremely unclear about personal values).

-Knowledge: Questions will assess concepts about driving presented in the DDA and control group website.

-Self-Efficacy: We will measure decision self-efficacy (one's self-confidence or belief in one's ability to make decisions) using the Decision Self-Efficacy Scale, as decision aids can increase self-efficacy. Transformed scores range from 0 (extremely low) to 100 (extremely high self-efficacy).

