Analysis for Aim 1: Analyses will be performed according to the principle of intention-to-treat. including all randomized drivers. Unless otherwise specified, hypothesis tests will be two-sided with alpha=.05, with 95% confidence intervals or p values reported. All canalyses will be performed using SAS/STAT® software. First, descriptive statistics will be computed for baseline patient characteristics, initially testing for differences between control and intervention groups (including for key covariates, Table 3.3). We will assess site effects by comparing demographic variables across the sites, using ANOVA for continuous measures and chi-square tests of proportions for categorical measures. If no statistically significant differences exist among sites. we will ignore site and formally test the differences in proportions or means as described below. If there are significant differences among sites, then (assuming enough events) we will use separate bivariate logistic regression models for each aim described below, with a fixed effect for site and with treatment arm as the main predictor. For longitudinal analyses, we will conduct logistic regression with unstructured correlation of generalized estimating equations (GEE) to account for the repeated observations for each participant. Statistical significance will be evaluated at one-sided p<.05 level. Analyses of the DDA's longitudinal effects may be vulnerable to bias, as control arm participants may be exposed to intervention arm messages through exposure to available materials or courses related to driving safety or cessation (e.g., websites, physician counseling, AARP courses). We will assess exposure to other sources of information through structured questions. To mitigate the impact of this potential bias, we will adjust measurements of contamination as applicable. In all analyses, validation of distributional and parameterization assumptions will be checked and data transformations (e.g. logtransformations) or alternative methods will be implemented as appropriate.

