Aim 1a. Test the DDA's effect on immediate decision quality (measured by the Decisional Conflict Scale). Hypothesis 1a: More DDA participants will have high-quality (DCS<25) scores, compared to control, immediately after the intervention. Our primary outcome measure will be the proportion of participants with DCS score <25. We will perform multiple logistic regression to test the DDA's effect on decision quality. We are also interested in jointly modeling the proportion of family members with DCS score <25, so a bivariate logistic regression model will be used for analysis to allow assessment of marginal effects of the intervention on patients and family members, as well as their concordance/discordance in decision quality. In the small pilot trial of Australian drivers with dementia, mean DCS score scores decreased from 22.5 to 7.5 (out of 100) after the DA; should we find that DCS score distributions do not allow dichotomization based on the cut-point of 25, we will instead compare means between the groups. Missing data for the primary measure should be minimal, given that this will be obtained at enrollment. Additional analyses will include examining components of decision quality to identify changes in

AUTO Study Protocol: Version Date: 12/22/21 PI: [name], MPH COMIRB No: 19-0059 measures like knowledge, values-concordance, or self-efficacy, as they may shed light on the mechanisms underlying decision-making about driving.

Family member data: In addition to the analysis under 1a, we will examine the degree of concordance (or discordance) within driver-family dyads on various measures, including current versus desired level of family involvement in driving retirement process (part of the driving questionnaire). To evaluate agreement we will look at the kappa coefficients at baseline and at follow-up points, as well as apply this class of repeated-measure concordance correlation coefficients. For longitudinal data, we will examine changes across the other time points (6, 12, 18, 24 months) using GEE after adjusting covariates.

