**Analysis for Aim 2**: We will first test for interaction between DDA effect and each subgroup stratifying factor. We will then use separate stratified subgroup analyses to examine the effects of potential influential cognitive or affective factors on the effect of the DDA (using DCS score, the primary outcome from Aim 1a). As in Aim 1, we will first evaluate demographic characteristics and site effects; all comparisons within subgroups will be between DDA and control groups, using intention-to-treat analysis. The main analysis for each subgroup variable will be an unadjusted test of the intervention by subgroup variable interaction in a statistical model appropriate for the particular outcome (DCS score); specifically, separate multiple logistic models will include intervention group, subgroup, and an intervention-by-subgroup interaction as

AUTO Study Protocol: Version Date: 12/22/21 PI: [name], MPH COMIRB No: 19-0059 factors. Potentially confounding variables (e.g., age, gender) will also be examined in separate multivariable logistic models for each sub-aims.

Aim 2a. Compare the effect of the DDA on decision quality in older drivers with versus without cognitive impairment. Hypothesis 2a: The impact of the DDA will be greater among those without cognitive impairment, as they are able to process the DDA's explanation of facts and options to facilitate a decision. We will examine interaction between cognitive function and the DDA's immediate effect on decision quality (DCS score) by dichotomizing cognitive function into impaired (comprising MCI and dementia) non-impaired. For our initial analyses, we will compare impaired versus non-impaired and run separate simple logistic regression models for each group to determine how cognitive function impacts the relationship between treatment group (DDA or control) and decision quality, as measured by DCS scores. For each cognitive function subgroup, the outcome variable of interest will be the dichotomized decision quality measure (DCS <25 versus DCS  $\geq$ 25), and the intervention group status will be the independent variable. Should we have adequate sample size, we may examine the MCI and dementia subgroups independently.

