Aim 2b. Compare the effect of the DDA on decision quality in older drivers with maintained versus impaired decisional capacity. Hypothesis 2b: The impact of the DDA will be greater among those with retained decisional capacity. Decisional capacity scores (range: 0-8) will be examined as a linear variable with controlling for confounding by cognitive function. We will examine the distribution of decisional capacity among the study's 300 participants to define subgroups; participants will be divided into 2-3 subgroups based on decisional capacity scores. As with cognitive impairment above, a simple logistic regression model will be run for each decisional capacity subgroup with dichotomized decision quality measure as the outcome of interest and intervention group status as the independent variable. Additionally, a non-stratified analysis can be conducted in which decisional capacity score is included as an additional independent variable model.

Aim 2c. Compare the effect of the DDA on decision quality in older drivers who are more versus less attitudinally ready for transitions. Hypothesis 2c: The impact of the DDA will be greater in those readier for mobility changes, as defined by lower ARMT scores, as they are "primed" for decision-making (Figures 3.1 and 3.2). We will follow methods similar to Aim 2a, using logistic regression to examine interaction between ARMT score and the DDA's effect on DCS scores by dichotomizing ARMT into high (mean>3.57) versus low/medium (mean 1-3.56). Depending on the distribution of ARMT scores in our sample, we may examine those with low ARMT scores (mean<2.3), as this group may be more open to mobility changes.

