Sample Size: Our target sample size for Aim 1 (n=300 older drivers; 150 DDA and 150 control) was chosen to allow detection of a 20-40% difference between the DDA and control arms (depending on underlying proportions for each of the treatment arms) for the primary Aim 1a measure (DCS score <25; Figure 3.5) at a power of 90% and a 0.05 significance level, while allowing for 10% loss to follow-up. Our overall sample size also allows for stratified

analyses (Aim 2). Estimates for the effect of the driving DDA on behavior among older drivers do not exist, so our assumption of a 20-40% difference is conservative (prior work with other DAs has found an effect size of 40-80% on DCS between groups). For **Aim 2**, pilot work suggests estimates ~30% of participants will have cognitive impairment and 30% will have high ARMT scores (as described above). A stratified sample size of 90 should allow us to detect a 30% difference between the DDA and control groups, at 80% power (see Figure 3). For **Aim 3**, we estimate needing 15-20 interviews per stakeholder group (n=20 older drivers and family members/study partners; n=20 healthcare providers; n=20 experts in the field of older adult driving safety) to reach the "saturation point" (where additional interviews are unlikely to reveal

AUTO Study Protocol: Version Date: 12/22/21 PI: [name], MPH COMIRB No: 19-0059 new themes) while allowing for adequate group diversity. Please note the older drivers and

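### The Aim 2 interaction tests use only the DCS cut at 25; a prespecified interaction test on the 0-100 score would usually be more powerful and needs no new data

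*Combined protocol and SAP*

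**What the plan says.** Under Analysis for Aim 2 the interaction is the lead test: "The main analysis for each subgroup variable will be an unadjusted test of the intervention by subgroup variable interaction in a statistical model" suited to the outcome, which is named there as the DCS score. The next clause fixes the model family: "specifically, separate multiple logistic models will include intervention group, subgroup, and an intervention-by-subgroup interaction as" factors. For Aim 2a, "the outcome variable of interest will be the dichotomized decision quality measure (DCS <25 versus DCS" of 25 or more. Aim 2b fits a model in each capacity subgroup "with dichotomized decision quality measure as the outcome of interest and intervention group status as the independent variable". Aim 2c follows Aim 2a with logistic regression. Table 3 scores the DCS as below 25 for hypotheses 1a, 2a, 2b and 2c alike.

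The reason for the cut is in the Decision Conflict entry under Immediate outcomes: "Scores <25 (out of 100 total) are associated with implementing decisions". Aim 1a allows a switch to means if "DCS score distributions do not allow dichotomization based on the cut-point of 25, we will instead compare means between the groups". That provision is not repeated for Aim 2.

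The only power statement in the text for Aim 2 is in Sample Size: "A stratified sample size of 90 should allow us to detect a 30% difference between the DDA and control groups, at 80% power". It concerns the arms within one stratum, not an interaction.

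**The concern.** An interaction test compares two treatment effects, so it is far less precise than the overall arm comparison, and a 30/70 split weakens it further. Reducing a 16-item, 0-100 score to yes or no discards more information exactly where the trial has least to spare. Hypotheses 2a to 2c ask whether the DDA improves decision quality more in one group than in another, which is a question of degree that the full score can address.

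Finding out who benefits most is a stated goal of the trial. If a real difference between subgroups is missed, the DDA may be targeted badly, or the finding of no difference may be read as evidence that it works alike in everyone.

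**Working it through.** **Inputs from the plan.** 300 drivers, 1:1, or 300 × 0.9 = 270 after the 10% loss (Sample Size). About 30% cognitively impaired and 30% with high ARMT scores (Sample Size), so with 300 drivers the strata have 45 and 105 per arm. By default "hypothesis tests will be two-sided with alpha=.05" (Analysis for Aim 1).

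**Assumptions, because the text gives no values.** Control proportion with DCS<25 of 30% to 60%, the same in both strata. Effect only in the larger stratum. Roughly normal score with equal SD, so that a change from p1 to p2 equals a mean shift of d = probit(p2) − probit(p1) SDs.

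**1. The plan's own figure.** 45 per arm, worst case 35% vs 65%. The null SE is √(2×0.5×0.5/45) = 0.1054 and the alternative SE is √(2×0.35×0.65/45) = 0.1006. Then (0.30 − 1.96×0.1054)/0.1006 = 0.93, which gives 82% power. With 10% loss (40.5 per arm) it is 78%. The stated 80% reproduces.

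**2. Interaction on the cut.** With nL and nS per arm in the larger and smaller strata, the variance of the log-odds interaction is 1/(nL p1 q1) + 1/(nL p2 q2) + 2/(nS p1 q1), where q = 1 − p. For 40% to 60% and N = 300:
- log odds ratio = 2 ln 1.5 = 0.811
- variance = 2/(105×0.24) + 2/(45×0.24) = 0.265, SE 0.514
- ratio 1.577, power = Φ(1.577 − 1.96) = 35%

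**3. Interaction on the score, same case.** d = 0.507 SD. Variance = 2/105 + 2/45 = 0.0635, SE 0.252. Ratio 2.011, power = Φ(2.011 − 1.96) = 52%.

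**4. Other cases by the same formulas.**

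| N | Effect in larger stratum | Cut | Score | Loss (points) |
|---|---|---|---|---|
| 300 | 40% to 60% | 35.1% | 52.0% | 16.9 |
| 270 | 40% to 60% | 32.2% | 47.9% | 15.8 |
| 300 | 35% to 65% | 64.9% | 86.4% | 21.5 |
| 270 | 30% to 60% | 58.8% | 83.4% | 24.6 |
| 300 | 60% to 90% | 87.6% | 98.3% | 10.7 |

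Over the whole assumed range, a 20-point effect has 32% to 45% power on the cut and 48% to 65% on the score. A 30-point effect has 59% to 88% and 83% to 98%. Analysis for Aim 1 also contains a one-sided 0.05 sentence, after the longitudinal methods. Under that rule the loss at N = 300 is 16 to 18 points for the 40% to 60%, 35% to 65% and 30% to 60% cases.

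**5. How far the size moves.** For a normal score:
- Interactions of 0.4 to 0.8 SD with control proportions of 30% to 70% lose 10 to 25 points.
- Widening the control proportion to 20% to 80% takes the loss up to 33 points.
- An interaction of 0.2 SD can lose as little as 2 to 3 points, because both tests then have very little power.

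For bounded, skewed (beta) scores, simulation with control means of 22.5 to 35 and SD 15 to 20 lost about 4 to 21 points. Further settings near the pilot means lost about 1 to 15.

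**6. What the score cannot do.** For an interaction of 0.6 SD at N = 300, 0.6/0.252 = 2.381 and power is Φ(0.421) = 66%, still below 80%.

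**7. The floor.** Suppose unimpaired drivers move from a mean of 15 to 8 and impaired drivers from 40 to 25 (assumed), with similar odds ratios for DCS<25. In simulation the logistic interaction rejected in about 4% to 6% of runs. An unadjusted mean interaction rejected in about 54% to 59%, in the direction opposite to hypothesis 2a.

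**The case against.** The strongest reply is that DCS<25 is the trial's own definition of a high-quality decision (Aim 1a), so Aim 2 properly asks whether the primary endpoint is modified. A mean-score interaction has a different target, and step 7 shows that it can be significant merely because one subgroup starts near zero. This stands. It means that the logistic interaction should remain a reported test and that the score-based test needs baseline adjustment.

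The size is also open to challenge. The Aim 1a section quotes pilot means of 22.5 falling to 7.5 on a scale bounded at 0, where a normal score with equal SD is doubtful. The gain shrinks there, and if the DDA also narrows the spread of scores the cut can capture part of that change. The 30% share is given for Aims 2a and 2c only; the subgroups for Aim 2b are to be defined from the data. It can also be argued that Aim 2 inherits the Aim 1a fallback to means. Even so, that fallback is triggered only if the cut is unworkable, and it is not a prespecified interaction test on the score.

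A reader might infer more: that the loss is a fixed 13 to 25 points, that the cut makes a null Aim 2 result likely, or that the 80% in Sample Size is wrong. The documents support none of these. The loss depends on quantities that they do not give. For a 30-point effect, power on the cut is 59% to 88%. The 80% reproduces for the within-stratum comparison that it describes.

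**Conclusion.** The point holds as a cheap improvement, not as an error in the plan's figures. Every Aim 2 interaction test is written for DCS cut at 25, and none is prespecified on the score.

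The cut costs about 10 to 25 points of interaction power if the score is roughly normal, the split is 30/70 as in Aims 2a and 2c, N is 270 to 300, 30% to 60% of controls are below 25, and the effect is confined to one stratum. It costs about 1 to 20 points with bounded, skewed scores near the pilot means. A score-based test does not rescue Aim 2 from small interactions, since at 0.6 SD or less it stays below 80% power. It also does not replace the DCS<25 comparison, which carries the plan's definition of a good decision.

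**What to change.** For Aims 2a to 2c, prespecify a linear model of immediate post-intervention DCS (0-100) on arm, subgroup variable and arm-by-subgroup, adjusted for pre-intervention DCS, with robust standard errors. Report the difference in mean effect with its 95% CI. Keep the DCS<25 logistic interaction as a reported test beside it, and state in advance how the two will be read together. Where they disagree, examine the baseline and post-intervention distributions by subgroup for a floor effect before interpreting either. Add a sentence giving interaction power under stated assumptions. Leave Aim 1a unchanged.

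The cost is plan wording and a few lines of code. No new data are needed, because Table 3 already collects the DCS from drivers before and after the intervention. The downside is that two scales with different targets are reported, and baseline adjustment reduces but does not remove the chance that a mean-scale interaction reflects the floor of the score.

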## Study Design and Research Method

We will use a multi-site, two-armed randomized controlled trial of older drivers (n=300; ≥70 years) from clinical settings, and one family member each (n=up to 300), with longitudinal follow-up. Our goals are to test how much the DDA improves outcomes and identify who benefits most from the DDA. Our evaluation of the DDA's efficacy (Aim 1) and its relative effect in subgroups (Aim 2) corresponds to Stage II in the NIH Stage Model for Behavioral Intervention Development. Our findings from Aims 1 & 2 could identify necessary refinements (Stage I) and inform future efficacy, effectiveness or implementation trials.

**Sites:** For this multi-site trial, we plan to include clinics associated with three sites to provide geographic diversity, along with access to populations with racial and ethnic variability. We request that COMRIB serve as the single IRB for this research study, with other IRBs ceding oversight.

- **University of Colorado Health:** Participants will be recruited primarily from three clinics associated with University of Colorado Health.
  - UCHealth Senior's Clinic Aurora, CO
  - o UCHealth Internal Medicine Anschutz clinic Aurora, CO
  - UCHealth Internal Medicine Lowry clinic Denver, CO
- University of California-San Diego: Participants will be recruited primarily from five clinics and four practices associated with University of California San Diego
  - UCSD The Shiley Eye Clinic San Diego, CA
  - UCSD Neurological Institute San Diego, CA
  - UCSD Memory Disorders Clinic San Diego, CA
  - UCSD Senior Medicine Clinic San Diego, CA
  - Memory Aging and Resiliency Clinic San Diego, CA
  - UCSD Internal Medicine Practice San Diego, CA (four practices)
- Indiana University: Participants will be recruited primarily from 29 primary care clinics associated with the Indiana University School of Medicine.
  - Indiana Health Indianapolis, IN (20 clinics)
  - Eskenazi Health Indianapolis, IN (9 clinics)
    - Eskenazi Health is not a part of Indiana University and will not be actively engaged in research. They will be participating as a recruitment site only.

**Recruitment:** We will follow methods used successfully in the LongROAD cohort study. Research assistants (RAs) at each site will identify potentially-eligible older drivers by screening the electronic health records of clinic patients to identify patients aged  $\geq$ 70 years with at least one relevant medical diagnosis.

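### Aim 2 makes the interaction test its main analysis, but the Aim 2a and 2b paragraphs also give effect modification to separate stratum models, which for 2a and 2c can mislead through stratum size alone

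*Combined protocol and SAP*

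**What the plan says.** The opening paragraph of Analysis for Aim 2 tests the interaction first, calls it the main analysis for each subgroup variable, and specifies a logistic model with arm, subgroup and their product. Stratified analyses follow, with no condition on what the interaction shows.

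The sub-aim paragraphs differ from one another:

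- **Aim 2a** says interaction will be examined. It then says the initial analyses will "run separate simple logistic regression models for each group to determine how cognitive function impacts the relationship" between arm and decision quality.
- **Aim 2b** says that "a simple logistic regression model will be run for each decisional capacity subgroup", and adds an optional unstratified model with the capacity score as a further predictor. No product term is named in this paragraph.
- **Aim 2c** asks for an interaction by logistic regression, using methods similar to Aim 2a.

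The secondary insight analysis also follows the Aim 2a procedure.

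The Sample Size paragraph expects about 30% of drivers to be cognitively impaired and 30% to have high ARMT scores. Its only power statement for Aim 2 is within a stratum: "A stratified sample size of 90 should allow us to detect a 30% difference between the DDA and control groups", at 80% power. Study Design and Research Method gives as a trial goal to "identify who benefits most from the DDA".

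**The concern.** Two analyses are asked the same question. The interaction model compares the treatment effects directly. The separate models each test whether the effect is zero in one stratum; setting a significant result beside a non-significant one says nothing formal about whether the effects differ, and the contrast depends heavily on stratum size.

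In 2a and 2c the predicted direction coincides with the size imbalance: the hypotheses expect more benefit in unimpaired drivers and in those readier for transition, the groups expected to hold about 70% of the sample. A size artefact would therefore look like confirmation.

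For 2b the difficulty is different. In a model that only adds the capacity score as a predictor, the treatment effect is forced to be the same at every score, so it cannot test effect modification. Read alone, the 2b paragraph leaves only the per-subgroup models to address the hypothesis.

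At stake is a statement about who benefits from the aid, which the trial is meant to supply for later tailoring.

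**Working it through.** **Inputs from the documents.** Sample size: "n=300 older drivers; 150 DDA and 150 control". Shares of about 30% in 2a and 2c give strata of 0.30 × 300 = 90 and 0.70 × 300 = 210, or about 45 and 105 per arm. Planned effect on the proportion with DCS <25: 20 to 40 points overall, 30 points for a stratum of 90. Sidedness: "hypothesis tests will be two-sided with alpha=.05" unless stated otherwise.

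**Assumptions.** The readable text gives no control rate, so 20% to 50% is used. The control rate is taken as equal in the two strata, with 1:1 allocation within each. The outcome is measured at enrolment, so no loss is applied.

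**Formula.** Power = Φ[(d − 1.96·SE0)/SE1], with SE0 = √(2p̄(1−p̄)/n) and SE1 = √([p0(1−p0) + p1(1−p1)]/n), n per arm.

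**Step 1: the plan's own figure.** With 45 per arm and d = 0.30, power is 82.4% (35% v 65%) to 86.0% (20% v 50%). With a continuity correction, 20% v 50% needs exactly 90 drivers. The difference detectable at 80% power is 27.6 to 29.2 points. The stated figure reproduces, as a comparison within one stratum.

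**Step 2: same 20-point effect in both strata (40% v 60%).**

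- 105 per arm: SE0 = 0.0690, SE1 = 0.0676; (0.20 − 0.1353)/0.0676 = 0.958; power 83%.
- 45 per arm: SE0 = 0.1054, SE1 = 0.1033; (0.20 − 0.2066)/0.1033 = −0.064; power 47.5%.
- Significant in the large stratum only: 0.831 × (1 − 0.475) = 44%.
- Significant in the small stratum only: 0.475 × (1 − 0.831) = 8%.

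**Step 3: range over control rates of 20–50%** (formula, and simulation of Wald log-odds tests, two-sided 0.05).

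| True effect, both strata | Large stratum only |
|---|---|
| 20 points | 41–45% |
| 30 points | 14–19% |
| 40 points | 1–3% |

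The reverse pattern at 20 points occurs in 6–8% of trials. With one-sided testing at 0.05 (the Aim 1 text also contains "Statistical significance will be evaluated at one-sided p<.05 level", after the longitudinal models), the 20-point figure is 31–36%.

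**Step 4: the interaction test in the same simulated trials.** It rejects in about 4–5%, about 2.5% in the hypothesised direction. With equal control rates, equal percentage-point effects also mean equal odds ratios, so this is a true null on both scales. At 20 points, about 38–42% of trials show the large-stratum-only pattern together with a non-significant interaction. In those trials the main analysis shows no difference while the stratum models appear to show one.

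**Step 5: when effects really differ.** Interaction power is about 31–46% for 30 v 10 points and about 61–76% for 30 v 0. A non-significant interaction is therefore quite likely even then, which adds to the temptation to read the stratum models instead.

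**Step 6: scale.** The interaction is on the odds scale, while Sample Size plans Aim 2 in percentage points. If control rates differ between strata, the two can rank groups differently. As an invented illustration, 70% to 85% is +15 points with OR (0.85/0.15)/(0.70/0.30) = 2.43; 40% to 60% is +20 points with OR (0.60/0.40)/(0.40/0.60) = 2.25.

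**The case against.** The strongest reply is that the plan already handles this. The interaction comes first, is called the main analysis, and is specified with its product term for each subgroup variable, which covers 2b as well. Aim 2a mentions interaction just before the disputed wording, and Aim 2c uses the word itself. No sentence says strata will be compared by significance. All of that stands, and it limits the point. A reader might infer that Aim 2 has no valid test of effect modification, or that the planned analysis is wrong in about 4 trials of 10. The documents support neither: under the stated main analysis the error is about 5%, and the larger figure applies only if stratum significance is used for inference.

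A reader might also infer that every Aim 2 hypothesis favours a larger stratum. That is not supported for 2b: no subgroup shares are given, the cut is left to the observed distribution, and a median split is among the options. With an equal split, one-stratum-only significance at 20 points is symmetric, about 18–22% in each direction.

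The effect size also matters. Twenty points is the low end of the planned range, and the pattern is rare at 40. Nor does the plan propose withholding the aid from anyone; it describes findings that inform refinement and later trials.

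What the reply does not answer is the wording. The stratified models run whatever the interaction shows, Aim 2a gives them the task of determining effect modification, and nothing calls them descriptive or settles a disagreement.

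**Conclusion.** The point holds as an inconsistency in the Aim 2 text, not as the absence of an interaction test. The Aim 2a wording, carried into 2c and the insight analysis, and the 2b paragraph without a product term leave room for conclusions that the main analysis would not support.

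For 2a and 2c the exposure, if stratum significance were compared, is about 41–45% at 20 points, 14–19% at 30 and 1–3% at 40, against about 5% for the interaction test. These figures rest on strata of about 210 and 90, an equal true effect, equal control rates of 20–50% (assumed), and two-sided 0.05. No such figure can be fixed for 2b, because its subgroup sizes are not specified. The text is worth correcting before analysis; design and data collection are unaffected.

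**What to change.** 1. Reword Aim 2a so that any claim of a different effect by cognitive function rests on the interaction estimate and its confidence interval. Carry the same wording into Aim 2c and the insight analysis.
2. Write the treatment-by-capacity product term explicitly into Aim 2b. Keep the model with capacity as an added predictor only as a description of its association with the outcome.
3. Present stratum results as estimates with confidence intervals, and state that they will not be compared by significance.
4. Report each contrast also as a difference between percentage-point effects, the scale on which Sample Size plans Aim 2.

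The cost is a few sentences and one extra contrast per sub-aim, with no new data. The downside is fewer apparently positive subgroup statements, since the interaction has limited power at this sample size.
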